3.1.1 Study periods

The study comprises the following consecutive periods:

Screening period: Lasts approximately 6–7 weeks; starts with the signing of the informed consent form (ICF; at the screening visit) and ends the day before subject randomization.

Treatment period: Lasts approximately 6 months. Starts on the day of subject randomization (randomization visit) and ends at the EOT visit (Month 6). It will consist of site visits at Month 1, Month 3, Month 5 and Month 6 and telephone call visits at Month 2 and Month 4.

The EOT visit will take place at Month 6 (or earlier in the event of premature discontinuation).

Whenever possible, the EOT visit should take place 1 day after the last dose of study treatment but no later than 7 days after the last dose of study treatment.

Post-treatment observation period (PTOP): Subjects who discontinue study treatment prematurely will enter into the PTOp, which starts on the day after the last dose of study treatment, and ends at latest at the Month 6 PTOp visit.

During this period, all assessments except PK will be performed. They will be performed at the time of the originally scheduled visits [[Table 6](#)].

Post-treatment safety follow-up (FU) period: The FU period is applicable to all subjects except those who enter the open-label extension (OLE) study. It starts on the day after the last dose of study treatment:

- For female and non-fertile male subjects: it includes 1 safety FU telephone call (FU1) taking place approximately 1 month after the last dose of study treatment;
- For fertile male subjects: it includes 2 safety FU telephone calls taking place approximately 1 month (FU1) and 3 months (FU2) after the last dose of study treatment.

Subjects who complete the 6-month double-blind treatment period will be proposed to enroll into an OLE study conducted under a separate protocol (provided the OLE study protocol has been approved in the country/site by regulatory authorities and Ethics Committees [ECs] / Institutional Review Boards [IRBs]).

Subjects who discontinue study treatment prematurely for any reason should be subsequently treated according to local standard-of-care at the investigator's discretion and will be followed in the PTOp until the originally scheduled Month 6 visit.

[figure not shown]
For an individual subject, the End-of-Study (EOS) is defined as follows:

- For subjects who enter the OLE study, the EOS corresponds to the EOT visit;

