10.3.2.5 Supportive analyses

A series of additional analyses based on the modified BPI-SF3 score data are presented below and will support the primary endpoint results by analyzing the primary endpoint variable using various other methods and assumptions.

Responder analysis

Using subject responses from the modified BPI-SF3, a response variable (yes/no) will be calculated based on a reduction of at least 30% from baseline to Month 6 in the modified BPI-SF3. Subjects who have a missing modified BPI-SF3 score at Month 6 for any reason will be considered as non-responders.

The Cochran-Mantel-Haenszel (CMH) test stratified by sex and ERT treatment status at screening (treated vs not treated) will be used to test for a difference in the proportions of responders at Month 6 between treatment groups.

The treatment effect (lucerastat vs placebo) will be expressed in terms of the common odds ratio (OR_c) and corresponding 95% CI. An OR_c > 1 will indicate a response to treatment in favor of lucerastat as compared to placebo.

Homogeneity of the treatment effect across strata will be investigated using the Breslow-Day test.

Impact of the use of different analysis sets

An analysis on the PPS will be performed in order to assess the impact of important protocol deviations on the assessment of the primary endpoint. This analysis will especially address the issue about the lack of adherence to protocol or compliance to study treatment.

An analysis on the FAS may also be performed and will assess the impact of being randomized but not treated [see Section [10.1.8](#)].

Impact of data collected during use of significant rescue pain therapy

The modified BPI-SF3 scores of “neuropathic pain at its worst in the last 24 hours” on the days that a subject received any significant rescue pain therapy are substituted by the worst score of that subject during the double-blind treatment period. Monthly scores are then derived as described in Section 10.2.1 and the same analysis model as described in Section 10.3.2.2 will be applied.

Characterization of treatment effect over time

The treatment effect over time will be investigated by means of a mixed model for repeated measures (MMRM) on the available monthly scores.

Use of different cut-offs for the definition of a responder at Month 6

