## 2.1 Study periods

The study comprises the following consecutive periods as described in section 3.1.1 of the protocol:

**Screening period:** Lasts approximately 6–7 weeks; starts with the signing of the informed consent form (screening visit) and ends with the day before subject randomization. During this period, the subjects will start completing an electronic diary (eDiary) on a daily basis.

**Treatment period (double-blind):** Lasts approximately 6 months, starts on the day of subject randomization (randomization visit) and ends at the EOT visit. It will consist of site visits at Month 1, 3, 5 and 6 and telephone call visits at Month 2 and 4.

The EOT visit will take place at Month 6 (or earlier in the event of premature treatment discontinuation). Whenever possible, the EOT visit should take place 1 day after the last dose of study treatment but no later than 7 days after the last dose of study treatment.

**Post-treatment observation period (PTOP):** Subjects who discontinue study treatment prematurely will enter the PTOp which starts on the day after the last dose of study treatment and ends at the latest at the Month 6 PTOp visit. During this period, all assessments except PK will be performed. They will be performed at the time of the originally scheduled visits.

**Post-treatment safety follow-up (FU) period:** The FU period is applicable to all subjects except those who enter the open-label extension (OLE) study. It starts on the day after the last dose of study treatment:

- For female and non-fertile male subjects: it includes 1 safety FU telephone call (FU1) taking place approximately 1 month after the last dose of study treatment.
- For fertile male subjects: it includes 2 safety FU telephone calls taking place approximately 1 month (FU1) and 3 months (FU2) after the last dose of study treatment.

Subjects who complete the 6-month, double-blind treatment period will be offered enrollment into an OLE study conducted under a separate protocol (provided the OLE study protocol has been approved in the country/site by regulatory authorities and Ethics Committees / Institutional Review Boards).

Subjects who discontinue study treatment prematurely for any reason should be subsequently treated according to local standard-of-care at the investigator's discretion and will be followed in the PTOp until the originally scheduled Month 6 visit.

[figure not shown]
For an individual subject, the End-of-Study (EOS) is defined as follows:

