### 15.2.2 Description of missing data

All available eDiary data collected from baseline (last four weeks prior to randomization), and after randomization and up to the Month 6 visit (i.e., during the treatment phase, after treatment discontinuation and during the FU and PTOP periods) will be used to calculate the monthly scores. All the data up to the Month 6 visit will be included in the primary analysis.

Despite the measures implemented to prevent missing data [described in protocol section 7.2.2.2.4], some missing data will occur in the daily measurements, possibly translating into missing monthly scores. In the next sections “missing data” will refer to missing monthly scores.

A summary of missing patterns can be presented for each treatment group as illustrated in [Table 10](#).

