#### ***15.2.5.4 Change from baseline to Month 6 where data on days with use of any significant rescue pain therapy are substituted by a worst score***

The modified BPI-SF3 scores of “neuropathic pain at its worst in the last 24 hours” on the days that a subject received any significant rescue pain therapy are substituted by the worst score of that subject during the double-blind treatment period. Monthly scores are then derived as described in Section 9.1 and the same analysis model as described in Section 15.2.3 will be applied.

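### In the rescue-therapy supportive analysis, a rescue day after the End-of-Treatment visit can be replaced by a better score than the one recorded, because only scores from the double-blind period can supply the replacement.

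*SAP*

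**What the plan says.** SAP 15.2.5.4 takes the daily neuropathic pain scores "on the days that a subject received any significant rescue pain therapy" and states that they "are substituted by the worst score of that subject during the double-blind treatment period". Monthly scores are then rebuilt and the primary model is refitted. Protocol 10.3.2.5 has the same rule. It moves straight from the substitution to the derivation of monthly scores, with no clause that keeps the recorded score when it is the worse one: "that subject during the double-blind treatment period. Monthly scores are then derived as described in Section 10.2.1". SAP Table 12 repeats the rule and gives its purpose as the impact of significant rescue pain therapy.

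SAP 2.1 labels the treatment period as double-blind and says that it "starts on the day of subject randomization (randomization visit) and ends at the EOT visit". It adds: "The EOT visit will take place at Month 6 (or earlier in the event of premature treatment discontinuation". Protocol 3.1.1 agrees: "The EOT visit will take place at Month 6 (or earlier in the event of premature discontinuation". Both documents define the PTOP as a separate period that runs up to the Month 6 PTOP visit.

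The days that can be substituted cover a longer span. SAP 9.5.2 and Table 9 identify rescue days from study day 1 and count them up to the Month 6 visit, with no restriction to days on treatment. SAP 15.2.2 confirms that diary data "after treatment discontinuation and during the FU and PTOP periods) will be used to calculate the monthly scores".

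**The concern.** The replacement value comes from one period, and the days being replaced can lie in a longer one. Within the double-blind period the rule cannot improve a score, because the worst score over a period is at least as bad as any single score in it. After the EOT visit that guarantee is lost. The recorded score is overwritten, but it is not among the scores from which the worst is chosen.

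Table 12 lists no other supportive analysis of how rescue use affects the primary endpoint. Substituting a worst score is a deliberately unfavourable treatment of rescue days. If some substitutions are favourable, the analysis is not the conservative check that its wording suggests. The case is also foreseeable: lack of efficacy is a listed reason for stopping study treatment (SAP 8.2), and the individual pain plan and daily pain-medication diary continue through the PTOP (protocol 5.2.3.2.2 and 5.2.5.2).

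**Working it through.** The plan gives no figure for this rule, so there is none to reproduce. The check compares the two periods and then works through the averaging.

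**1. Periods**

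| Item | Runs from | Runs to | Source |
|---|---|---|---|
| Scores that can supply the worst value | Randomization visit | EOT visit | SAP 2.1, 15.2.5.4 |
| Days that can be rescue days | Study day 1 | Month 6 visit | SAP 9.5.2, Table 9 |
| Daily pain scores collected | Screening visit | Month 6 or Month 6 PTOP visit | Protocol 7.2.2.2.1 |
| Days in the Month 6 score | Month 6 visit − 28 | Month 6 visit − 1 | SAP 9.1, Table 4 |

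For a subject who completes treatment, the first two rows coincide. For a subject who stops early, they differ by the time from the EOT visit to Month 6. The EOT visit should be "1 day after the last dose of study treatment but no later than 7 days after the last dose of study treatment", so scores in those few days still count as double-blind although the PTOP has formally begun.

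**2. Direction**

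Let M be the subject's worst daily score in the double-blind period and d the recorded score on a rescue day. The substitution changes that day by M − d.

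- Rescue day up to the EOT visit: d ≤ M by definition, so the change is zero or upward.
- Rescue day after the EOT visit with d ≤ M: zero or upward.
- Rescue day after the EOT visit with d > M: downward, that is, an apparent improvement.

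Only the third case is a fault. One subject's window can contain both upward and downward changes.

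**3. Size for one subject (assumed scores)**

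With a complete diary, the mean of four weekly means is the mean of 28 days. If all 28 recorded scores equal d and k of the days are rescue days after the EOT visit:

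Month 6 score under the rule = [k × M + (28 − k) × d] / 28

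Take M = 7 and d = 9, so the recorded score is 9.0:

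- k = 7: (49 + 189) / 28 = 8.5
- k = 14: (98 + 126) / 28 = 8.0
- k = 28: 196 / 28 = 7.0

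Over M from 6 to 8, d from 8 to 10 and k of 7, 14 or 28, the error runs from 0 (M = 8, d = 8) to −4.0 points (M = 6, d = 10, k = 28).

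**4. Size for an arm (assumed frequencies)**

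One subject shifted by 2 points moves a planned arm mean by 2/66 = 0.03 (lucerastat) or 2/33 = 0.06 (placebo). With the approximate randomized numbers in SAP Section 2 (79 and 39), the figures are 2/79 = 0.03 and 2/39 = 0.05. If 2% to 15% of an arm were affected by 0.5 to 2 points each, its mean would move by 0.02 × 0.5 = 0.01 to 0.15 × 2 = 0.30 points towards improvement. The design difference in protocol 10.5 is 2 points between arms. The documents give no rate of early stopping followed by rescue, so these frequencies only span a range.

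**The case against.** The strongest reply concerns the meaning of the period. Protocol 3.1 and SAP Section 2 also describe every randomized subject as entering a double-blind treatment period of six months. If that planned interval is what SAP 15.2.5.4 means, PTOP scores can supply the worst value and the problem disappears. However, SAP 2.1 is where the period is defined, and it ends at the EOT visit. The PTOP is set apart there and in the protocol's two visit schedules. SAP 2.1 also offers the extension study to subjects who complete the six-month double-blind period, which implies that early stoppers do not complete it. The looser wording does not override this definition. At the least, the text needs to say which period is meant.

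The second reply is that the conditions are narrow, and this stands. The subject must stop early, continue the diary, have a rescue day after the EOT visit, and record a score above a maximum of daily worst-pain ratings. Protocol 6.6.1 reports attacks or crises one to four times a month in about 30–40% of subjects with neuropathic pain, so a high maximum may be reached even in a short treatment period. The full 2-point shift in the example needs all 28 window days to be rescue days scored 9.

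The third reply is that little depends on this analysis. It is one of several supportive analyses, and rescue use is also compared between arms as a yes/no endpoint and as an annualized rate (SAP 15.4.3). This also stands.

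**Conclusion.** The point holds as a defect in a stated rule, of minor importance. Under the definition in SAP 2.1, the substitution can lower a score on rescue days after the EOT visit and nowhere else. The illustrative effect on one affected subject's Month 6 score is 0.5 to 2.0 points for a double-blind worst of 7 and PTOP scores of 9. The effect on an arm mean is probably small but cannot be determined from the documents. The primary analysis, its missing-data sensitivity analyses and the testing sequence do not use this rule.

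A reader might infer more, and the documents do not support it:

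- That the error could be as large as the planned treatment effect. The 2 points in protocol 10.5 are a difference between arm means; a 2-point shift in one subject is not comparable.
- That the analysis favours lucerastat. The shift favours whichever arm has more rescue days after the EOT visit scored above the double-blind maximum, and that is unknown.
- That early stoppers who then need rescue are the specific target of the analysis. The stated purpose is the impact of rescue therapy in general. A conservative intent is itself inferred from the choice of a worst score.

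**What to change.** In SAP 15.2.5.4 and Table 12, on each rescue day use the worse of the recorded daily score and the subject's worst score in the double-blind treatment period. SAP 9.5.2 classes some days with missing diary entries as rescue days; where no score was recorded, use the worst double-blind score. The replacement can then never be better than what the subject reported.

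An alternative is to take the worst score from randomization to the Month 6 or Month 6 PTOP visit. This also removes the fault and is simpler to state. Its small downside is that off-treatment scores, possibly recorded after enzyme replacement therapy was started, could replace scores on rescue days during treatment. Earlier monthly scores, which feed the imputation model, would change as a result. The first option avoids this.

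The cost is one phrase in the SAP text, one in Table 12 and one line of derivation code. The departure from protocol 10.3.2.5 should be recorded in SAP Section 20, which already lists changes from the protocol. Changing the protocol text itself would need a formal amendment (protocol 12.6). The change should be made before unblinding.

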#### ***15.2.5.5 Repeated-measures analyses of monthly modified BPI-SF3 scores up to Month 6***

A mixed model for repeated measures (MMRM) will be used on the monthly change from baseline scores available at Month 1, Month 2, Month 3, Month 4, Month 5, and Month 6. The following terms will be included in the model: baseline modified BPI-SF3 score, treatment group, month, treatment group by month interaction and the two stratification factors sex and ERT treatment status at screening. An unstructured “UN” covariance structure will be primarily used for estimation of the correlation between responses

measured across the same subjects across multiple months (in the event of a convergence issue, a first order auto-regressive covariance structure will be used). The two study treatment groups will be compared at each month (with a primary interest in Month 6). The estimates of the differences in scores between treatment groups at each month will be reported with their 95% CIs. In addition, the adjusted means by treatment group at each month will be reported as estimates of the monthly scores across time.

This analysis will be implemented by the following SAS® code:

```
proc mixed;
  class subjid sex ertstatus treatment month;
  model change = sex ertstatus bsl treatment month treatment*month / ddfm=kr;
  repeated month / type = UN subject=subjid(treatment);
  lsmeans treatment*month;
  slice treatment*month / sliceby=month pdiff cl;
run;
```

#### ***15.2.5.6 Month 6 responders/non-responders analyses using different cut-offs of the percent reduction from the baseline score***

A supportive analysis will derive the response at Month 6 by using cut-offs for response (20, 40, 50%) different from the 30% cut-off used in Section 15.2.5.1. The cut-offs of 40 and 50% have been mentioned in the literature [Dworkin 2008] as substantial change in pain. This analysis will be conducted as the analysis described in Section 15.2.5.1 (i.e., subjects with missing modified BPI-SF3 score at Month 6 will be considered as non-responders).

#### ***15.2.5.7 Empirical cumulative distribution function plots***

Empirical cumulative distribution function (eCDF) plots will be provided for the absolute change from baseline to Month 6 and the percent change from baseline to Month 6 in the modified BPI-SF3 score by treatment group.

#### ***15.2.5.8 Determination of an anchor-based value for the change in modified BPI-SF3 when using PGIC as external anchor***

In order to assess the clinical relevance in the context of the FD of the cut-off of 30% used in the responder analysis, the change in modified BPI-SF3 at Month 6 will be compared to the classification as responder/non-responder when using the PGIC at Month 6 visit as an external criterion. The methods used will be in line with previous publications in other diseases [Farrar 2010] and an FDA guidance for interpretation of patient-reported outcomes [McLeod 2011]. The two PGIC questionnaires (PGIC-DS, PGIC-PS) will be analyzed separately using the same approach.

These analyses will be conducted on the set of subjects with data available for both the change in modified BPI-SF3 at Month 6 and for the considered PGIC questionnaire at Month 6 visit. The analyses will be conducted on the two study treatment groups combined.

The change in modified BPI-SF3 at Month 6 will be expressed in two different ways: as absolute change from baseline and as percent change from baseline.

The polyserial and Spearman correlation coefficients between the change in modified BPI-SF3 at Month 6 and PGIC at Month 6 visit will be reported with their 95% CI.

This analysis will be implemented by the following SAS® code:

```
proc corr spearman fisher polyserial;  
  with pgicchange;  
  var percentchange;  
run;
```

The confidence limits of the polyserial correlation coefficient will be derived as the coefficient  $\pm 1.96$  multiplied by its standard error. The confidence limits of the Spearman correlation coefficient will be derived using Fisher's z-transformation.

The correspondence between change in modified BPI-SF3 at Month 6 and the PGIC at Month 6 visit will be graphed by displaying the distribution (using box-plots) of modified BPI-SF3 at Month 6 within each PGIC level.

Three different response variables (yes/no), each corresponding to levels of improvement as characterized by the PGIC at Month 6 visit will be examined: "minimally improved" or better (PGIC = 1, 2 or 3); "much improved" or better (PGIC = 1 or 2); or "very much improved" (PGIC = 1).

For each of the three PGIC response variables and each of the two types of change in modified BPI-SF3 (absolute change or percent change), the empirical probability density function (ePDF) and the eCDF of each type of change in BPI-SF3 will be graphically represented for responders and non-responders according to the considered PGIC response variable. The ePDF will show on the y-axis, for each of the two categories (responder, non-responder) of the PGIC response variable the probability of observing a given modified BPI-SF3 change (kernel density estimated curves) vs the change in modified BPI-SF3 (on the x-axis). The eCDF will show, for each of the two categories (responder, non-responder) of the PGIC response variable, the total number of subjects, the cumulative proportion of subjects (on the y-axis) who reach a given modified BPI-SF3 change or less vs the change in modified BPI-SF3 (on the x-axis); horizontal lines at  $y = 50, 10, 25, 75,$  and  $90\%$  will illustrate the median change and the 10th, 25th, 75th, and 90th percentiles of the change in modified BPI-SF3 for each response category. The ePDF and eCDF will also be presented using the original non-collapsed PGIC categories.

In addition, the empirical receiver operating characteristic (ROC) will be generated by calculating the sensitivity and 1-specificity in each  $2 \times 2$  table using the number of subjects who achieve each observed level of change (or of percent change) in modified BPI-SF3 and the pre-selected level of improvement in PGIC as the outcome. For each empirical ROC curve, the area under the curve will be reported. Assuming an equal importance for

sensitivity and specificity, the optimal cut-off based on observed data will be defined as the point at the intersection of a 45° line with the ROC curve (i.e., the point minimizing the distance to the upper left corner). The corresponding sensitivity, specificity and agreement percentages (accuracy, positive predictive value, negative predictive value), will be reported.

**15.2.5.9 Determination of an anchor-based value for the change in modified BPI-SF3 when using change in PGIS-D or change in PGIS-P as external anchor**

In order to further assess the clinical relevance of the cut-off of 30% in the context of FD, the change in modified BPI-SF3 at Month 6 will be compared to the classification as responder/non-responder (improvement / no improvement [defined in Section 9.6.5]) when using the change in PGIS-D and the change in PGIS-P at Month 6 visit as external criterion.

These analyses will be conducted on the set of subjects with data available for both the change in modified BPI-SF3 at Month 6 and for the change in PGIS-D at Month 6. The analyses will be conducted on the two study treatment groups combined.

The change in modified BPI-SF3 at Month 6 will be expressed in two different ways: as absolute change from baseline and as percent change from baseline.

For each type of change in modified BPI-SF3, a box plot (including the individual data points) will represent the change in PGIS-D on the y-axis (ranging from -3 to +3) vs the change in modified BPI-SF3 on the x-axis and the corresponding polyserial and Spearman correlation coefficients will be provided.

Similarly as described in Section 15.2.5.8, ePDF and eCDF plots will be produced using the “improvement / no improvement” categories as defined in Sections 9.6.3 and 9.6.5 as well as each distinct category (i.e., 3-category improvement, 2-category improvement, 1-category improvement, no change, 1-category worsening, 2-category worsening, 3-category worsening).

The same series of analyses will be repeated on the change in PGIS-P.

For each of the two PGIS anchor scales, the following two tables will be provided [Table 13 and Table 14].

